7.1. Summary of Study Design

[figure not shown]
Patients will come to the investigator site for Visits 2, 4, 6, 8, 11, 12, ~~and 13~~, and 801 for various study assessments during the treatment period. Patients will be contacted over the telephone for Visits 3, 5, 7, 9, ~~and 10~~, and ~~801~~ (described as “Telephone Visits” in Section 7.2.2.2) to assess their response to study drug (including 4-point SMBG, AEs, and hypoglycemia) and/or to further

adjust insulin doses, if needed. Insulin dose adjustments will be done in both treatment arms to help patients achieve glycemic targets (HbA1c <7%, preprandial capillary BGs 79 to 126 mg/dL [4.4 to 7.0 mmol/L]) while minimizing/avoiding hypoglycemia. Patients will come for a clinic visit at Visit 13 for their final assessments at the completion of 24 weeks. At approximately 4-weeks post-treatment endpoint, patients will have a final ~~telephone~~ teleclinic visit (Visit 801), at which information will be collected according to the Study Schedule (Attachment 1).

End of study (trial) is the date of the last visit or last scheduled procedure shown in the Study Schedule for the last active patient in the study.

Figure ABES.7.1 illustrates the study design.

7.2.2.2.1. Patients Eligible for Randomization at Visit 2

- Eligible patients will be randomized to 1 of 2 treatment groups by a random assignment based on Visit 1 HbA1c, prestudy treatment with basal-bolus insulin or premixed insulin, and prestudy treatment with metformin or not metformin or acarbose usage (metformin only, acarbose only, or neither). For patients with prestudy treatment of metformin or acarbose (excluding those taken both) prior to Visit 1, their concomitant OAM will be discontinued at Visit 2.

7.2.2.3. Telephone Visit 1

Between each investigator-site visit, patients will have a telephone visit with the investigator or designee at Visit 3, 5, 7, 9, and 10, and 801.

7.2.2.4. Study Visits (Visit 3 to Visit 13 or Early Discontinuation)

Patients will come to the investigator site at 2-week intervals between Visit 2 and Visit 8. From Visit 8 to Visit 13, patients will come to the clinic at 6-week intervals. Visit 801 is a 4-week follow-up ~~telephone~~clinic visit (Attachment 1).

7.2.2.5. Follow-up Visit (Visit 801)

Patients will ~~receive a telephone call~~come to the investigator site approximately 4 weeks after the last treatment visit, at which time information will be discussed and recorded according to the Study Schedule (Attachment 1). Patients who discontinue early from the study will undergo all

end-of-study procedures and complete Visit 801 as outlined in Attachment 1. These data will be collected and stored for future reference/analyses, if needed.

7.2.3. Blood Glucose Monitoring Plan

- Patients will be instructed to complete 2 separate 7-point SMBG profiles in the 1-week period prior to each office visit from Visit 2 to Visit 13 (or at ED) (preferably most recent readings). At Visit 801, only 4-point SMBG is required to be collected. The SMBG profiles will consist of:
 - before the morning meal, midday meal, and evening meal; 2-hour postprandial measurements for the morning, midday meal, at bedtime and 3 am.

Throughout the study, patients will be expected to routinely check their fasting, premeal, and bedtime BG values daily to help assess the need for dose adjustments and to guide dosing of the mealtime/fast-acting insulin lispro (Attachment 5). Patients may be requested by investigators (as they deem necessary) to perform more intensive self-monitoring, if clinically indicated. Both 4-point and 7-point SMBG values will be recorded in the diaries and transcribed into the eCRF at the office visit ~~and at Visit 801~~ (Attachment 1 and Attachment 5).

8.2. Exclusion Criteria

- [17] Have taken any oral antihyperglycemic medications (OAMs) within 3 months prior to Visit 1. Except for those patients with metformin or acarbose at a stable dose for more than 90 days prior to Visit 1 (excluding those taken both), ~~they~~their concomitant OAM will be discontinued metformin at randomization before the study treatment.

9.3. Method of Assignment to Treatment

At Visit 1, patients will be assigned a patient number, and at Visit 2, those who are eligible to participate in the study will be assigned by stratified randomization to 1 of the 2 treatment arms, in a ratio of 1:1, via random assignment using the interactive web response system. To achieve between-treatment group comparability, patients will be stratified by screening HbA1c stratum (<8.5%, ≥8.5%), pre-study treatment (Lantus®-bolus, other basal-bolus, premixed insulin), and pre-study metformin usage ~~(yes or no)~~ or acarbose usage (metformin only, acarbose only, or neither).

9.4. Rationale for Selection of Doses in the Study

At randomization, in the patients who were administered with basal-bolus therapies before enrollment, QD LY2963016 will be started at the same doses as the QD prestudy basal insulin. For those patients with BID prestudy basal insulin as part of basal bolus regimen, the total daily prestudy insulin dose will be reduced by 20% at randomization to LY2963016 or insulin glargine, therefore, the study basal insulin dose will be 80% of the prestudy basal insulin dose. Insulin lispro will be administered with meals at the same doses as the patient's prestudy mealtime insulin dose while avoiding hypoglycemia, as determined by unit-to-unit conversion. Based on the patient's prestudy mealtime insulin regimen relative to his/her lifestyle, the investigator could

translate the patient's previous mealtime insulin regimen so that the patient's prestudy mealtime insulin is replaced with a similar dose of insulin lispro to be used during the study. During the course of the study, the patient's mealtime insulin does will be adjusted and optimized by investigators. During the course of the study, the patient's mealtime insulin doses will be adjusted and optimized by the investigator, ~~as he or she is encouraged to do SMBG readings before meals and instructed to titrate his or her mealtime insulin dose as guided by those premeal readings, in addition to investigator directed insulin dose adjustments guided by the previous days' glucose patterns.~~ Study participants will administer mealtime insulin doses before meals to provide insulin coverage for the meal, as well as a correction dose if the premeal BG reading is above target.

10.3.1.1. Serious Adverse Events

~~The investigator does not need to actively monitor patients for adverse events once the trial has ended, unless provided otherwise in the protocol. However, if an investigator becomes aware of SAEs occurring to a patient after the patient's participation in the trial has ended, the investigator should report the SAEs to the sponsor, regardless of the investigator's opinion of causation, and the SAEs will be entered in the pharmacovigilance system at the sponsor. Investigators are not obligated to actively seek AEs or SAEs in subjects once they have discontinued and/or completed the study (the patient summary CRF has been completed). However, if the investigator learns of any SAE, including a death, at any time after a subject has been discharged from the study, and he/she considers the event reasonably possibly related to the study treatment or study participation, the investigator must promptly notify Lilly.~~

10.4.2.1. Nonpharmacogenetic Biomarker Evaluations

This study will employ sample collection. Samples will be collected for nonpharmacogenetic biomarker investigation where local regulations allow. ~~Blood-Fasting serum~~ samples will be collected at the times specified in the Study Schedule (Attachment 1).

~~Samples-Fasting samples~~ being collected will be used to measure C-peptide to support trial interpretation.

12.1. Determination of Sample Size

Based on the primary objective, to show noninferiority of LY2963016 to Lantus® at the 0.40% noninferiority margin (NIM), 109 completers per arm (218 total) are needed at 24 weeks. This calculation assumes no treatment difference in HbA1c between LY2963016 and Lantus®, a common standard deviation (SD) of 1.05% for change from baseline in HbA1c, a two-sided significance level of 0.05, and over 80% power. Assuming a 15% dropout rate at 24 weeks, the required number of randomized patients is 129 per arm (258 total).

12.2.4. Concomitant Therapy

Concomitant medications, including previous therapies for diabetes, will be summarized by different categories and treatment group using the FAS population. All concomitant therapies that originally mapped using the WHODRUG dictionary in the ~~InFuseClintrial~~ database will be

further classified using anatomical, therapeutic chemical code for reporting purpose. Analyses will use test Fisher's Exact Test or Pearson's Chi-square test.

12.2.6. Primary Efficacy Outcome and Methodology

The primary efficacy outcome will be the change in HbA1c level from baseline to 24 weeks. The primary analysis will be a likelihood-based, MMRM approach, treating the data as missing at random (MAR) for the FAS population. The MMRM model will evaluate the change from baseline to each postbaseline visit in HbA1c level as the dependent variable with treatment (LY2963016, Lantus®), pre-study treatment (Lantus®-bolus, other basal-bolus, premixed insulin), and pre-study metformin ~~usage (yes or no)~~ or acarbose usage (metformin only, acarbose only, or neither), visit, and interaction between visit and treatment as fixed effects; the baseline value of HbA1c as a covariate; and a random effect for patient. The MMRM model will be carried out using the observed margins (OM) option in SAS. Using this option weights the levels of the independent or stratification variables according to the observed marginal distribution. This will provide least-squares means (LSMeans) for these outcomes that are more representative of the patient population recruited in this study.

A second secondary analysis of the primary efficacy outcome will use an ANCOVA model with FAS population. The ANCOVA model will include treatment, pre-study treatment, and pre-study metformin or ~~usage (yes or no)~~ or acarbose usage (metformin only, acarbose only, or neither) as fixed effects and the baseline value of HbA1c as a covariate. The ANCOVA model will be carried out using the OM option in SAS. If the 24-week HbA1c value is missing, the last postbaseline value will be carried forward and used in the analysis. This creates the 24-week endpoint value for HbA1c using the LOCF methodology. If there are no HbA1c data after the date of randomization, the endpoint will be considered missing and the patient will not be included in the analysis.

12.2.9.2. Adverse Events

Adverse events will be listed by patient, system organ class, Medical Dictionary for Regulatory Activities® (MedDRA) preferred term, severity, and relationship to the study disease, drug, device, or procedure for all patients. Adverse events will be summarized as treatment-emergent adverse events (TEAEs) for the FAS. Treatment-emergent adverse events are defined as events that are newly reported after first study treatment following randomization, or reported to worsen in severity from ~~randomization~~ baseline. The proportion of patients experiencing each TEAE will be presented by preferred term, system organ class, and treatment group. The proportion of patients experiencing each TEAE that are assessed as possibly related to the study disease, drug, device, or procedures will also be summarized. The number and proportion of patients will be presented and compared by treatment using Fisher's exact test or Pearson's chi-square test for the FAS.

12.2.9.3. Hypoglycemic Events

The rate of hypoglycemic episodes per 30 days and per year (total, severe, nocturnal, and others) will be analyzed at baseline, titration, maintenance, and overall study periods and at endpoint

using the Wilcoxon test. In addition, the hypoglycemia rates will also be analyzed using a negative binomial model for the FAS population with terms for treatment, baseline HbA1c, prestudy treatment, and prestudy metformin or acarbose usage. The offset variables are log of patient's treatment duration/30 and log of patient's treatment duration/365.25 for the models analyzing hypoglycemia rate per 30 days and per year, respectively.

12.2.9.4. Laboratory Measures

Chemistry and hematology laboratory measures will be summarized as change from baseline to each postbaseline visit. The continuous measures and change from baseline values to 24 weeks will be analyzed using the ANCOVA model with treatment, prestudy treatment, and prestudy metformin or acarbose usage as fixed effects and the baseline value of HbA1c and the baseline of the response variable as covariates. The ANCOVA model will be carried out using the OM option in SAS.

12.2.10. Subgroup Analyses

- Prestudy metformin or acarbose use: (metformin only, acarbose only or neither)

The change in HbA1c from baseline to 24-week endpoint will be analyzed using MMRM with treatment, visit, prestudy treatment, prestudy metformin or acarbose usage, subgroup, subgroup-by-treatment interaction, subgroup-by-visit interaction, treatment-by-visit interaction, and treatment-by-visit-by-subgroup interaction as fixed-effects, the baseline value of HbA1c as a covariate, and a random effect for patient for the FAS. If the subgroup is one of the stratification variables, then the subgroup will only be included once in the model. A significant treatment-by-subgroup interaction ($p < .05$) may be indicative of a differential treatment effect across levels of the subgroup, necessitating further exploration of the nature of the interaction.

Attachment 1. Protocol ABES Study Schedule

Description of Event	Visit														
	1	2	3*	4	5*	6	7*	8	9*	10*	11	12	13	801±	ED#
Week of Study	-2	0	1	2	3	4	5	6	8	10	12	18	24	28	
Allowable Deviation (Days) ^a	±7 ^a		±2 ^a	±3 ^a	±3 ^a	±7 ^a	±7 ^a								
Telephone Visit			X		X		X		X	X				✕	
Clinic Visit	X	X		X		X		X			X	X	X	X	X
Clinic Assessments															
Concom. Meds ^{b†}	X	X	X ^b	X	X ^b	X	X ^b	X	X ^b	X ^b	X	X	X	X [†]	X
Adverse Events ^{b†}	X	X	X ^b	X	X ^b	X	X ^b	X	X ^b	X ^b	X	X	X	X [†]	X
Hypoglycemic Episodes ^{b†}		X	X ^b	X	X ^b	X	X ^b	X	X ^b	X ^b	X	X	X	X [†]	X
4-point SMBG ^{b†}			X ^b		X ^b		X ^b		X ^b	X ^b				X [†]	
Study Drug/Device/Training and Education^d															
Distribute Study Diary	X	X		X		X		X			X	X	X		X
Transfer Diary Data to eCRF (InForm™)															
Insulin Therapy Dose (day prior to visit) [‡]		X	X	X	X	X	X	X	X	X	X	X	X	X [†]	X
Telephone Visit 4-point SMBG [‡]				X		X		X			X			✕ [†]	
Lab Assessments															
Serum Samples for Biomarkers (Fasting) ⁱ		X ⁱ						X ⁱ					X ⁱ		Xⁱ
Anti-gGlargine aAntibody †Titer		X		X				X			X		X		X
Fasting Serum Glucose ⁱ		Xⁱ											Xⁱ		Xⁱ

Patients who discontinue early from the study will complete Visit 801.

b Adverse events, hypoglycemic episodes, concomitant medications, and the last three available 4-point SMBG profiles reported at telephone visits should be recorded on the eCRF at the next office visit ~~or at Visit 801~~. The 4 points are: before morning, mid-day, evening meals, and at bedtime.

i ~~Information will be collected during a telephone visit and will be recorded on the eCRF. Site documentation will serve as the source for this telephone visit, as the patient will not be returning the paper diary to the site.~~ The measurements should be done fasting before breakfast.

Attachment 2. Protocol ABES Clinical Laboratory Tests

Hematology^a	Clinical Chemistry^a
Hemoglobin	Serum Concentrations of:
Hematocrit	Sodium
Erythrocyte count (RBC)	Potassium
Leukocytes (WBC)	Total bilirubin
	Direct bilirubin
Platelets	Indirect bilirubin
Neutrophils, segmented	Alkaline phosphatase
Lymphocytes	Alanine aminotransferase (ALT)
Monocytes	Aspartate aminotransferase (AST)
Eosinophils	Blood urea nitrogen (BUN)
Basophils	Creatinine
Other	Albumin
Pregnancy Test ^b	Albumin
Hemoglobin A1c ^a	Fasting serum glucose
Anti-glargine Antibodies ^a	
Serum for nonpharmacogenetic biomarkers (C-peptide)	-

4.1. Primary Objective

The primary objective of this study is to test the hypothesis that LY2963016 QD is noninferior to Lantus[®] QD by a margin of 0.40%, as measured by change in hemoglobin A1c (HbA1c) from baseline to 24 weeks, when used in combination with premeal insulin lispro administered thrice a day (TID).

4.2. Secondary Objectives

The secondary objectives of the study are as follows:

- To test the hypothesis that Lantus[®] is noninferior to LY2963016, as measured by change in HbA1c from baseline to 24 weeks, when used in combination with premeal insulin lispro (TID) (this secondary objective is tested with a gated approach).
- To compare the safety of LY2963016 to Lantus[®] (proportion of patients with detectable of anti-glargine antibodies, hypoglycemia and injection site reaction) when used in combination with premeal insulin lispro.
- To compare change in HbA1c at 6, 12, and 18 weeks between LY2963016 and Lantus[®] when used in combination with premeal insulin lispro
- To compare 7-point self-monitored blood glucose (SMBG) profiles at baseline, 2, 4, 6, 12, 18, and 24 weeks between LY2963016 and Lantus[®] when used in combination with premeal insulin lispro
- To compare percentage of patients with HbA1c <7% and percentage of patients with HbA1c ≤6.5% at 6, 12, 18, and 24 weeks between LY2963016 and Lantus[®] when used in combination with premeal insulin lispro
- To compare LY2963016 to Lantus[®] when used in combination with premeal insulin lispro with regard to the following measures
 - inpatient blood glucose (BG) variability
 - basal and prandial insulin dose
 - weight change

To compare patient-reported outcomes (PRO) between LY2963016 and Lantus[®] as measured by responses to the Insulin Treatment Satisfaction Questionnaire (ITSQ).

5. A Priori Statistical Methods

5.1. Determination of Sample Size

5.1.1. Sample Size Section from the Protocol

Based on the primary objective, to show noninferiority of LY2963016 to Lantus® at the 0.40% noninferiority margin (NIM), 109 completers per arm (218 total) are needed at 24 weeks. This calculation assumes no treatment difference in HbA1c between LY2963016 and Lantus®, a common standard deviation (SD) of 1.05% for change from baseline in HbA1c, a two-sided significance level of 0.05, and over 80% power. Assuming a 15% dropout rate at 24 weeks, the required number of randomized patients is 129 per arm (258 total). This sample size is noted as the minimum sample size required in the study.

Blinded sample-size reestimation (bSSR) may be performed when approximately 40% of the subjects have been enrolled in the study and finished 24-weeks of treatment, or about 6 months prior to the completion of enrollment, depending on which occur first by team assessment. This reestimation will use a statistical model to estimate the variability in the change in HbA1c from baseline to 24 weeks using all available patient HbA1c values at the time of data cutoff. The estimate of variability will then be used to recalculate the sample size that would be needed to have 80% power for a NIM of 0.4%, assuming no difference between treatments. The sample size from the study is constrained between a predefined minimum sample size of 258, and a maximum sample size of 400 patients. If the recalculated sample size is smaller than minimum sample size planned, the study will enroll to the minimum sample size. If the recalculated sample size is larger than the planned minimum sample size, the team will make a decision whether to increase sample size to the reestimated sample size, bounded by the predefined maximum, or accept the consequent reduction in power.

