12.1. Determination of Sample Size

Based on the primary objective, to show noninferiority of LY2963016 to Lantus® at the 0.40% noninferiority margin (NIM), 109 completers per arm (218 total) are needed at 24 weeks. This calculation assumes no treatment difference in HbA1c between LY2963016 and Lantus®, a common standard deviation (SD) of 1.05% for change from baseline in HbA1c, a two-sided significance level of 0.05, and over 80% power. Assuming a 15% dropout rate at 24 weeks, the required number of randomized patients is 129 per arm (258 total).

Blinded sample-size reestimation may be performed when approximately 40% of the subjects have been enrolled in the study and finished 24-weeks of treatment, or about 6 months prior to the completion of enrollment, depending on which occur first by team assessment. This reestimation will use a statistical model to estimate the variability in the change in HbA1c from baseline to 24 weeks using all available patient HbA1c values at the time of data cutoff. The estimate of variability will then be used to recalculate the sample size that would be needed to have 80% conditional power for a NIM of 0.4%, assuming no difference between treatments. The sample size from the study is constrained by a predefined maximum sample size of 400 patients. If the recalculated sample size is smaller than sample size planned (258), the study will enroll to the sample size planned. If the recalculated sample size is larger than the planned sample size, the team will make a decision whether to increase sample size to the reestimated sample size. If the reestimated sample size is larger than the predefined maximum sample size, the team will increase the sample size to 400 subjects.

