5.1.2. Blinded Sample Size Re-estimation

A bSSR procedure will be utilized to ensure that the trial has an appropriate sample size to achieve the pre-specified power. This procedure is blinded, in that it does not use information on treatment assignments. Only pooled data from a blinded snapshot will be used to estimate the variance of the primary endpoint. Based on the estimated variability, the final study size will be calculated. The allowable range of the final sample size is constrained in a pre-specified manner, subject to the planned and maximum sample size. The bSSR procedure described below was evaluated via simulation and is efficient in determining the appropriate sample size under a range of possible scenarios without inflating type 1 error. The methodology and implementation details are described below.

The bSSR procedure has four steps,

- 1) At a blinded snapshot, a Bayesian predictive model will use the available data to generate predictions (multiple imputations) of all future HbA_{1c} data yet to be observed in the trial using the available data at the snapshot (see Section 5.1.2.2).

- 2) These predicted datasets will each be analyzed using the primary analysis model. The residual errors from each model will be used to determine a predictive distribution of the total variability of change in HbA_{1c} from baseline to the end of the study.
- 3) The predictive distribution of the variability will be used to determine the recommended sample size.
- 4) The study team will consider the recommended sample size and decide on the final sample size.

For practical reasons, the final sample size is constrained by a pre-specified minimum, N_{\min} , and maximum, N_{\max} . Therefore if the estimated final sample size is greater than N_{\max} , 400 is recommended. If the estimated final sample size is less than N_{\min} , 258 is recommended. The resulting estimated sample size is a recommendation, is non-binding, but represents the model estimate of the appropriate sample size. The final decision on the sample size would be subject to constraints from the maximum and minimum sample sizes. Factors influencing the final sample size are described in Section 5.1.2.4.

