5.1.2.3. Blinded SSR Methodology

At the time of the blinded SSR, all available HbA_{1c} data in the database will be used. The HbA_{1c} value for subject i , and time t_j is denoted as y_{ij} , the total duration of the study is d , the subject random effect is, s_i , and the residual error is, ϵ_{ij} . The model for HbA_{1c} a Bayesian Integrated Two-Component Prediction (ITP) (Fu, 2010) and is written as,

$$y_{ij} = (\theta + s_i + \epsilon_{ij}) \frac{(1 - e^{-kt_j})}{(1 - e^{-kd})}$$

with the between subject error,

$$s_i \sim N(0, \sigma_b^2),$$

and within subject error,

$$\epsilon_{ij} \sim N(0, \sigma_w^2).$$

This model is Bayesian and requires specification of prior distributions for each parameter. For each parameter, non-informative priors have been chosen,

$$k \sim \text{Uniform}(0.001, 10),$$

$$\theta \sim N(-1, 1000),$$

$$\sigma_b^2 \sim \text{IG}(0.01, 0.01),$$

and

$$\sigma_w^2 \sim \text{IG}(0.01, 0.01).$$

This Bayesian model will be fit using Markov Chain Monte Carlo (MCMC) with the OpenBUGS package in R. The MCMC algorithm will use one chain, with initial values for the parameters drawn from their corresponding prior distributions. An appropriate burn-in period will be used of at least 10,000 iterations to ensure that the MCMC chain has reached convergence. After the burn-in period, 10,000 MCMC samples will be obtained for all parameters in the model, as well as all missing y data. Therefore each MCMC sample contains a complete predicted dataset,

where all unobserved y data are imputed. These 10,000 predicted datasets will be used to estimate the variability in HbA_{1c}. To ensure independence of the MCMC samples, the chains will be thinned by at least 10 to ensure that the 10,000 selected samples are not highly correlated. Diagnostics will be assessed to ensure convergence of the chain.

For each of the 10,000 MCMC samples, the primary analysis described in Section **Error! Reference source not found.** (containing all terms other than treatment assignment), will be performed using the complete dataset corresponding to each imputation step. For each of these k analyses, $k=1$ to 10,000, the total variability will be estimated, as $\hat{\sigma}_{T,k}$ by evaluating the residual error of the model. For each value of $\hat{\sigma}_{T,k}$, the estimated sample size will be computed using the sample size formula introduced in the previous section for a non-inferiority trial,

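### The blinded sample-size re-estimation formula in the SAP is set for 95% power, although the protocol and SAP both state a target of 80%

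*SAP*

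**What the plan says.** The starting calculation in Protocol 12.1 and SAP 5.1.1 uses a true difference of zero, an SD of 1.05, two-sided α of 0.05, power just over 80% and 15% dropout. On that basis, "to show noninferiority of LY2963016 to Lantus® at the 0.40% noninferiority margin (NIM), 109 completers per arm (218 total) are needed at 24 weeks", or 258 randomised.

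For the re-estimation, SAP 5.1.1 says the new variance estimate is used to "recalculate the sample size that would be needed to have 80% power for a NIM of 0.4%, assuming no difference between treatments". Protocol 12.1 has the same target in slightly different words: "recalculate the sample size that would be needed to have 80% conditional power for a NIM of 0.4"%. SAP 5.1.2 gives the purpose: "A bSSR procedure will be utilized to ensure that the trial has an appropriate sample size to achieve the pre-specified power". The only power figure stated in either document is 80%.

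The formula is in SAP 5.1.2.1 and is repeated in 5.1.2.3. Both times its inputs are one-sided α = 0.025, β = 0.05, no true difference, a margin of 0.4 and 15% dropout. SAP 5.1.2.1 defines β as the type II error. The SD comes from the primary model without treatment, "by evaluating the residual error of the model".

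The result is then limited to the range 258 to 400. The SAP says of it: "The resulting estimated sample size is a recommendation, is non-binding, but represents the model estimate of the appropriate sample size". Protocol 12.1 is firmer at the upper limit: "If the reestimated sample size is larger than the predefined maximum sample size, the team will increase the sample size to 400 subjects". If the team does not take up an increase, SAP 5.1.1 has it "or accept the consequent reduction in power".

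**The concern.** A type II error of 0.05 is 95% power, so the formula does not aim at the target stated for it. Two statisticians working from the same snapshot could each follow the documents and report different sample sizes, one from the stated 80% and one from the printed β.

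A wrong β cannot bias the treatment comparison or change the non-inferiority rule, because the procedure uses no treatment assignments. What is at stake is the advice given to the team. It could be told that the trial is too small when it already meets its stated power, and that staying at 258 gives up power the plan requires. The result could be unneeded recruitment and delay.

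The two documents also disagree about a result above 400. The protocol commits the team to 400, while the SAP leaves it a recommendation.

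**Working it through.** **Inputs** (Protocol 12.1; SAP 5.1.1, 5.1.2.1 and 5.1.2.3): margin 0.4, true difference 0, SD 1.05, one-sided α 0.025 (z = 1.960), dropout 0.15, limits 258 and 400. For power, z = 0.842 at 80% and 1.645 at 95%.

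**1. Reproduce the plan's figure.** Completers per arm = 2 × (1.960 + 0.842)² × 1.05² / 0.4² = 2 × 7.849 × 1.1025 / 0.16 = 108.2, so 109. Then 109 / 0.85 = 128.2, so 129 per arm and 258 in total. The plan's number is an 80%-power number.

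**2. The SAP formula at the same SD.** N = 4 × (z₁₋α + z₁₋β)² × σ² / 0.4² / 0.85.

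- β = 0.20: 4 × 7.849 × 1.1025 / 0.16 / 0.85 = 254.5, which agrees with 258 once each arm is rounded up.
- β = 0.05 as printed: 4 × 12.995 × 1.1025 / 0.16 / 0.85 = 421.4, cut to 400.

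The ratio before the limits is 12.995 / 7.849 = 1.656 at any SD.

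**3. Where the limits take effect.** Solving for the SD, σ = √(N × 0.85 × 0.16 / 4) / (z₁₋α + z₁₋β).

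| | Increase above 258 starts at SD | 400 is reached at SD |
|---|---|---|
| β = 0.05 | 0.822 | 1.023 |
| β = 0.20 | 1.057 | 1.316 |

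**4. Recommended N after the limits, and the power 258 already gives.** Power = Φ(0.4 / (σ√(2/n)) − 1.960), with n = 258 × 0.85 / 2 = 109.65 completers per arm.

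| Estimated SD | N, β = 0.05 | N, β = 0.20 | Power with 258 |
|---|---|---|---|
| 0.85 | 276 | 258 | 93.6% |
| 0.94 | 338 | 258 | 88.3% |
| 1.00 | 382 | 258 | 84.2% |
| 1.05 | 400 | 258 | 80.5% |
| 1.10 | 400 | 279 | below 80% |
| 1.20 | 400 | 332 | below 80% |
| 1.30 | 400 | 390 | below 80% |

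At SD 1.05 the gap is 400 − 258 = 142 patients (+55%). With 400 randomised (170 completers per arm) power at SD 1.05 is 94.0%, so the upper limit does not deliver 95% there.

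**5. Allowing for the residual SD.** The formula uses the model's residual error, which may be smaller than 1.05. The documents do not say how much variance the model explains, so this is an assumption shown over a range. With raw SD 1.05 and explained share R², residual SD = 1.05 × √(1 − R²).

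| R² | Residual SD | N, β = 0.05 | N, β = 0.20 |
|---|---|---|---|
| 0% | 1.05 | 400 | 258 |
| 10% | 1.00 | 379 | 258 |
| 20% | 0.94 | 337 | 258 |
| 30% | 0.88 | 295 | 258 |
| 39% | 0.82 | 258 | 258 |

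The 400 limit is recommended only if the model explains less than about 5%. Some increase is recommended unless it explains about 39% or more.

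**The case against.** The strongest reply is that little depends on this. The re-estimation is optional, the SAP calls its output non-binding, and the size is bounded on both sides. The error can only raise the recommended number, so it cannot leave the trial smaller than planned or produce a false non-inferiority claim. All of that is true, and it limits the harm to the advice given.

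Two of the consequences depend on carrying a number from one section to another. The remark about reduced power in SAP 5.1.1 is correct if the number came from the 80% target stated there. It misleads only when the number comes from the formula in 5.1.2. Likewise, the protocol's rule for results above 400 starts at an SD of about 1.32 on the protocol's own 80% target. It starts at about 1.02 only if the SAP's number is fed into it. However, the SAP gives no other formula for the re-estimation.

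The actual SD is uncertain too. The primary model has a random patient effect, and SAP 5.1.2.3 speaks both of total variability and of residual error. If between-patient variance were left out, the SD could fall below 0.82, where both settings give 258. This affects how often the mismatch matters, not whether it exists.

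Extra patients would also help the reverse non-inferiority test needed to conclude equivalence. At SD 1.05 the chance of passing both tests is about 61% with 258 (2 × 0.805 − 1) and about 88% with 400 (2 × 0.940 − 1). That could be a reason for higher power, but neither document offers it.

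**Conclusion.** The point holds. The stated target is 80% and the formula that produces the recommendation uses 95%, with no justification. Because β = 0.05 is printed identically in two places, a text-extraction fault is unlikely. Only the 80% figure is consistent with the plan's own 258.

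For an estimated SD from about 0.82 to 1.06 the formula recommends an increase that the stated target does not need. From there to about 1.32 some increase is needed, but the recommendation is too large. Outside the range 0.82 to 1.32 the two settings agree after the limits. These thresholds rest on the SAP's formula with its stated margin, α and dropout. Which one applies depends on the residual SD found at the snapshot.

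The primary analysis and its error rate are not affected by the wrong β. Even so, it should be corrected before the snapshot: a pre-specified procedure has to give one answer, and here a confirmed planning assumption would lead to the maximum size. The differing rules above 400 are a real but separate inconsistency. The word conditional in Protocol 12.1 is only loose wording, since a blinded variance estimate has no interim treatment effect to condition on.

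**What to change.** Before the blinded snapshot:

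- Set β = 0.20 in the parameter lists of SAP 5.1.2.1 and 5.1.2.3. If 95% is intended, state and justify it in both documents, and note that 400 patients give about 94% at SD 1.05.
- Use one rule in both documents for a re-estimated size above 400, either binding or advisory.
- In Protocol 12.1, drop the word conditional from the power target.
- Confirm which β was used in the simulation cited in SAP 5.1.2, and repeat it only if it was not 0.20.

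The β correction is one parameter in two places and touches only the SAP. The wording change and the aligned rule may also require a change to the protocol text. No extra patients are needed.
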